6.1 Dosage and administration

Study drug is not being provided in this study as a government approved DAA regimen is being utilised.

6.2 Prior and concomitant medication

The treating clinician is responsible for assessing and managing the use of concomitant medications in line with the DAA regimen selected.

7. Study procedures

7.1 Visits and Procedures – main study

The following assessments must be conducted at study visits as per the schedule of assessments:

Finger-stick point of care	At all study visits. This point of care test will be performed using the Xpert®				
testing HCV RNA testing	HCV Viral Load assay on the Gene Xpert® II machine.				
(POC)					
Questionnaires	Behavioural survey, abbreviated behavioural survey and EQ-5D-5L				
Research sample	20mL EDTA and 4mL whole blood at baseline. 10mL EDTA at other study				
	visits if the HCV RNA point of care test is positive or invalid. 10mL EDTA at				
	re-viremia follow up visits.				
HCV sequencing (tested at	For relapse and reinfection as needed.				
Central lab using research					
sample after BSL)					
HCV RNA testing (local	Completed if the point of care test is positive or invalid.				
laboratory)					

The study physician is responsible for the treatment and monitoring of participants and their care. It is recommended that the following assessments are conducted as part of standard treatment monitoring, however this is at the physician's discretion. Any results that are generated from these assessments will be collected as part of the study data.

• Fibroscan or APRI value – within 12 months prior to baseline

The following assessments and procedures must be performed at each visit as specified below.

Baseline visit (Week 0)

- Informed consent
- Medical history
- Study questionnaires (Behavioural and EQ-5D-5L)
- HCV RNA (Finger-stick point of care testing)
- Research sample (20mL EDTA plasma & 4mL whole blood)
- HCV Sequencing (will be performed on the baseline research sample if re-viremia is detected at study follow up visits)

End of Treatment (ETR) – Variable (will depend on selected treatment regimen) (+/-14 days)

- Study questionnaires (Abbreviated Behavioural and EQ-5D-5L)
- HCV RNA (Finger-stick point of care testing)
- Research sample (EDTA plasma) (Only if the HCV RNA point of care test is positive or invalid)
- HCV RNA testing (Local Laboratory) (Only if the HCV RNA point of care test is positive or invalid)

Post Treatment Follow-up Visits

Post Treatment Week 12 (SVR12) – 12 weeks from ETR (+/- 14 days)

- Study questionnaires (Abbreviated Behavioural and EQ-5D-5L)
- HCV RNA (Finger-stick point of care testing)
- Research sample (EDTA plasma)) (Only if the HCV RNA point of care test is positive or invalid)
- HCV RNA testing (Local Laboratory) (Only if the HCV RNA point of care test is positive or invalid)

Post Treatment – SV24 (24 weeks post ETR), FU1 (36 weeks post ETR), FU2 (48 weeks post ETR), FU3 (60 weeks post ETR), FU4 (72 weeks post ETR), FU5 (84 weeks post ETR), FU6 (96 weeks post ETR), FU7 (108 weeks post ETR), FU8 (120 weeks post ETR), FU9 (132 weeks post ETR), FU10 (142 weeks post ETR) (+/- 14 days)

- Study questionnaires (Abbreviated Behavioural and EQ-5D-5L)
- HCV RNA (Finger-stick point of care testing)
- Research sample (EDTA plasma)) (Only if the HCV RNA point of care test is positive or invalid)
- HCV RNA testing (Local Laboratory) (Only if the HCV RNA point of care test is positive or invalid)

All participants who have suspected post treatment recurrence of viremia will have the following data and samples collected in addition to standard of care.

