Assessment/Procedure				
Study Visit	Re-viremia baseline	RFU1	RFU2	RFU3
Weeks from re-viremia baseline		2	4	8
Visit window (days)		+/- 14	+/- 14	+/- 14
HCV-RNA testing (Finger-stick point of care testing)		х	х	х
Research sample (EDTA plasma) (10mL)		х	х	х
HCV sequencing (tested at central lab using research sample collected at baseline) ^a	х			

^a For participants with post -treatment recurrence of viremia HCV sequencing will also be carried out on the research sample (10mL EDTA) that is collected at baseline of the main study

1. Background and rationale

In Australia, hepatitis C virus (HCV)-related morbidity and mortality have doubled in the past decade, with health care costs of \$220 million per annum¹. This is due to a large, ageing population with chronic infection (230,000), and low uptake of existing interferon-based therapy (1-2% per year) due to side-effects, and sub-optimal therapy efficacy. The majority of new (90%) and existing (80%) cases of HCV infection occur among people who inject drugs (PWID).

In the community, 15-20% of current PWID report recent (last month) receptive needle/syringe sharing². Qualitative research shows that decisions about sharing equipment are multi-factorial and can include issues ranging from service access (such as distance to service and opening hours), concerns about anonymity, perceptions that HCV is ubiquitous and unavoidable³ to socially-located concerns that promote use of sterile equipment such as a desire to avoid "track marks"⁴. There is no research that examines sharing of injecting equipment in those with successful therapy in either community or prison settings.

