10.1 Laboratory supplies and sample processing

Laboratory supplies for collection of research specimens (plasma and whole blood – all sites and PBMCS –

sub-study sites only) will be supplied by the Kirby Institute.

The following blood samples will be collected at time points specified in the schedule of assessments:

1. 10 mL EDTA plasma for HCV RNA testing and future HCV related research (20 mL will be

collected at baseline visit);

2. 4mL whole blood for human genomic DNA analysis collected at the baseline visit only.

Samples will be collected by sites and then processed and stored at -70°C or below at the site local

laboratory for bulk shipment to the Kirby Institute laboratory. Detailed sample processing instructions will

be provided in the laboratory manual.

EDTA plasma samples will be used for study endpoint analysis. HCV viral load will be measured using in-

house and commercial assays. Sequencing of the viral genome will also be performed as a more accurate

means of genotyping. Data generated from the sequencing may also be used to distinguish relapse from

reinfection and to examine the prevalence of mixed infection. Whole blood samples will be used to examine

host factors associated with viral clearance, including but not limited to HLA type, IL28-B, , IP-10, and other

biomarkers.

Sequencing

Sanger sequencing will be performed on all participants with HCV RNA relapse or reinfection in post

treatment follow up to distinguish HCV reinfection from viral relapse (detectable HCV RNA following HCV

virological suppression). Complementary RNA will be generated using SuperScript® VILO™ cDNA Synthesis

Kit (Life Technologies, Carlsbad, CA) with random hexamers. Sequencing of NS5A will be performed on all

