participants. A fragment of the HCV genome covering Core, Envelope-1, hypervariable region-1 and beginning of Envelope-2 (E2) will be amplified using a method previously described. Sequencing of NS3/4, NS5A, NS5B, and full-length next generation sequencing may also be performed. Purified amplicons will be sequenced using the Sanger method and sequence chromatograms processed using RECall: a fully automated sequence analysis pipeline. Subtypes will be determined using the Oxford HCV Automated Subtype Tool. Reverse transcription, PCR and sequencing reaction and thermal cycling conditions will be performed as previously described. Further, Sanger sequencing and next generation sequencing will be performed among samples with persistent infection at risk of HCV mixed infection (e.g. treatment non-response).

HCV RNA point of Care testing

Point of care testing for HCV RNA detection will be performed at each visit using the Xpert® HCV Viral Load assay for samples collected by finger-stick capillary whole-blood as described below.

The capillary whole-blood sample is collected from participants via a finger-stick [MiniCollect® Safety Lancet (Order Number 450429), Greiner Bio-One, Monroe, Frickenhausen, Germany] using procedures recommended by the World Health Organization³¹ and collected into a 100µL minivette collection tube [Minivette® POCT 100µl (Order number 17.2111.100), Sarstedt, Nümbrech, Germany]. The Xpert® HCV Viral Load assay is being evaluated as part of this study and is therefore only being used for research purposes, not for diagnostic purposes. As this assay is only being used for research purposes the results and a positive HCV RNA or invalid point of care test should be confirm by a local lab hepatitis C HCV RNA test the Xpert® HCV Viral Load assay will not be given to participants.

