Sample Size: Overall, based on previous reports of HCV reinfection among recent PWID³⁰, and assuming loss to follow-up is 20% per year, it is estimated that the overall reinfection rate will be 8/100 p-yrs (95%CI 5.7-10.7; 478 p-yrs of follow-up; 38 reinfections). Overall (225 with successful therapy, 38reinfections), we will have 80% power to detect a hazards ratio (HR) of 2.47 or greater (with alpha=0.05) for a variable 50% prevalent (e.g. ongoing injecting drug use).

Secondary Objectives:

4) To evaluate the proportion of participants with undetectable HCV RNA at 12 weeks post end of

treatment (SVR12) following DAA HCV therapy among PWID with chronic HCV infection and recent

injecting drug use;

5) To evaluate the proportion of participants who complete treatment;

6) To evaluate the proportion of participants with undetectable HCV RNA at the end of treatment

Hypothesis 2.1: Reduced response to DAA therapy among recent PWID will be predicted by previous

treatment experiences, cirrhosis, baseline mixed HCV infection and resistance associated substitutions.

Outcome: The primary endpoint for this aim is the proportion of participants with a treatment response

(measured by SVR, undetectable HCV RNA 12 weeks after the completion of therapy).

Statistical analysis: The proportion of people with a response to HCV therapy will be evaluated. Factors

associated with treatment response (as measured SVR) will be assessed by univariate and multivariate

logistic regression analyses. Factors hypothesised to be associated with response to DAA therapy are:

injecting behaviours (recent injecting drug use prior to and during treatment and type of drug injected),

clinical factors (opioid substitution treatment, HCV regimen, fibrosis stage), and virological factors (HCV

genotype, baseline mixed HCV infection, presence of resistance associated variants).

Sample size: Assuming an overall SVR of 90% (225 of 250), the 95% confidence intervals (95%CI) around

this estimate will be 86.0 to 92.8%. This study will have robust power to examine the effect of treatment

setting on SVR: e.g. 80% power to detect an odds ratio of 1.87 or greater (alpha=0.05) for a variable that

is 50% prevalent (i.e. community vs. prison).

Collateral research

Objective: To evaluate injecting behaviours and injecting cessation following successful DAA therapy.

Hypothesis: Daily injecting drug use and needle and syringe borrowing will decrease following the initiation

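### Sections 7.1, 7.2 and the recurrence schedule conflict with Section 10.1 on whose baseline sample is sequenced, and no section commits to measuring baseline mixed infection in responders without recurrence, although the SVR model uses it

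*Protocol*

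**What the plan says.** **Where the exposures are used.** In Section 11, Hypothesis 2.1 says that a reduced response will be predicted by previous "treatment experiences, cirrhosis, baseline mixed HCV infection and resistance associated substitutions". The logistic model for SVR in the same section lists, as virological factors, HCV "genotype, baseline mixed HCV infection, presence of resistance associated variants". Exploratory objective 5 is the prevalence of resistance associated substitutions.

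**Who is sequenced, by the visit schedule.** The baseline visit list in Section 7.1 reads: "HCV Sequencing (will be performed on the baseline research sample if re-viremia is detected at study follow up visits". The procedures table in the same section gives the trigger as "For relapse and reinfection as needed". Section 7.2 lists sequencing only for participants with recurrence. The footnote to the recurrence schedule says that, for these participants, "HCV sequencing will also be carried out on the research sample (10mL EDTA) that is collected at baseline of the main study". The main Schedule of Assessments has no sequencing row.

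**Who is sequenced, by Section 10.1.** The Sequencing paragraph opens with a set defined by outcome: "Sanger sequencing will be performed on all participants with HCV RNA relapse or reinfection in post" treatment follow-up. Two sentences later it says "Sequencing of NS5A will be performed on all" participants, with no sample or time point named. Sequencing of other regions, and full-length sequencing, is optional. On mixed infection it adds that Sanger and "next generation sequencing will be performed among samples with persistent infection at risk of HCV mixed infection (e.g. treatment non-response").

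**The concern.** A regression of SVR12 on a baseline exposure needs that exposure measured in responders and non-responders alike, by a rule that does not look at the outcome. Under the visit schedule, whether a baseline sequence exists depends on what happens after treatment. A responder who stays HCV RNA negative is never sequenced, and one who is later reinfected is. The responders available for comparison would then be a subset chosen for later reinfection, not a sample of responders.

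The analysis plan cannot repair this, because no analysis rule supplies an exposure that was never assayed. At stake are the odds ratios for two of the four predictors in Hypothesis 2.1 and the reading of objective 5 as a description of the cohort. The Background argues for surveillance of resistance and mixed infection among people who inject drugs, and a set made up of recurrences cannot provide that.

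**Working it through.** The protocol states no figure for the number sequenced, so there is none to reproduce. The check compares the sections and counts from the protocol's own planning numbers.

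**Inputs (Section 11, sample size paragraphs).** 250 enrolled; 225 with SVR (90%); 38 expected reinfections among the 225.

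**1. Predictors in Hypothesis 2.1**

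- Cirrhosis: in the model, as fibrosis stage.
- Previous treatment experience: not in the model's factor list.
- Resistance: in the model. It is measured in responders only if the NS5A sentence in Section 10.1 means the whole cohort and the baseline sample.
- Mixed infection: in the model. No section commits to measuring it in responders without recurrence.

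**2. Who has a baseline sequence if the visit schedule is followed**

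- Non-responders: 250 − 225 = 25.
- Responders later reinfected: about 38.
- Sequenced: 25 + 38 = 63, and 63/250 = 25%.
- Responders not sequenced: 225 − 38 = 187, and 187/225 = 83%.

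Both 25 and 38 are approximate. Time at risk starts at end of treatment, so some reinfections could come before SVR12. If a missing SVR12 result is counted as failure, that participant need not have had recurrent viraemia.

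**3. Precision.** With equal exposure prevalence in the two groups, the variance of the log odds ratio is proportional to 1/n(non-responders) + 1/n(responders). Efficiency relative to sequencing all 250:

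- 38 responders: (1/25 + 1/225)/(1/25 + 1/38) = 0.0444/0.0663 = 0.67.
- 100 responders: (1/25 + 1/225)/(1/25 + 1/100) = 0.0444/0.0500 = 0.89.

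The protocol gives no exposure prevalence, so a range is assumed. The odds ratio detectable with 80% power (two-sided 0.05, 25 non-responders) is:

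| Assumed prevalence in responders | 225 responders sequenced | 38 responders sequenced |
|---|---|---|
| 5% | 5.5 | 8.8 |
| 10% | 4.1 | 6.0 |
| 20% | 3.4 | 4.7 |

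**4. Bias.** The right-hand column treats the 38 as a random sample of responders, which they are not. The odds ratio for exposure, non-responders against sequenced responders, equals the one against all responders multiplied by

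(exposure odds in all responders)/(exposure odds in later-reinfected responders).

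The Background links mixed infection to ongoing high-risk behaviour, and the same behaviour leads to reinfection, so a factor below 1 is plausible for mixed infection. As an illustration only, assume a prevalence of 10% in all responders and 20% in those later reinfected. The factor is then (0.10/0.90)/(0.20/0.80) = 0.111/0.250 = 0.44, so the odds ratio would be less than half its proper value. For resistance the documents give no basis for a direction.

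**The case against.** The strongest reply is the NS5A sentence in Section 10.1. Read as the whole cohort at baseline, it puts NS5A resistance on record in responders, and objective 5 would not rest on recurrences alone. This stands as far as it goes. A reader of Section 7.1 alone might infer that resistance is sequenced only in recurrences, and the documents do not support that as a settled fact. However, the sentence follows one about participants with relapse or reinfection and may mean only them. It names no sample, covers NS5A alone, and on the wide reading contradicts Sections 7.1 and 7.2. For resistance the defect is therefore a conflict between sections, not a proven absence.

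On mixed infection, an earlier paragraph of Section 10.1 says that EDTA plasma will be sequenced as a more accurate means of genotyping, and that the data may be used to look at the prevalence of mixed infection. It does not confine this to recurrences. Non-response is also only an example in the mixed-infection sentence, so a reader who infers that this testing is capped at non-responders goes too far. Even so, the wording is permissive and adds no defined set of samples from responders.

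It is also too strong to say that responders have no exposure value, or that no odds ratio could be computed, since about 38 responders would have a sequence. The difficulty is that this subset is selected and small.

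The reach is limited as well. The primary reinfection incidence and the three secondary proportions are untouched. Factors associated with SVR12 and resistance prevalence are listed as exploratory objectives, although Section 11 places Hypothesis 2.1 under the secondary objectives.

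**Conclusion.** The point holds as a conflict between sections for resistance and as a missing commitment for mixed infection. If the visit schedule governs, baseline sequence is observed conditional on outcome: about 63 of 250 have one and about 187 of 225 responders (83%) do not. The odds ratio for mixed infection, and the one for resistance unless NS5A is sequenced in the whole cohort at baseline, would then be biased and imprecise, and objective 5 would describe participants with recurrence. The counts rest on the protocol's assumed 90% SVR and 38 reinfections, and on every non-responder being sequenced. The detectable odds ratios and the bias factor rest on assumed prevalences.

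Full sequencing would remove the selection but not the limit set by about 25 non-responders: at the assumed prevalences, only odds ratios of about 3.4 to 5.5 or more would be detectable.

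The omission of previous treatment experience from the factor list is a minor mismatch of wording. A reader might infer that the data are not collected, but medical history is taken at baseline and regimen choice depends on previous treatment, so nothing shows that.

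**What to change.** Reconcile Sections 7.1, 7.2 and 10.1 and the recurrence schedule so that baseline sequencing for resistance and mixed infection does not depend on outcome. State the sample, the regions and the set of participants. There are two ways to do it:

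- Sequence the stored baseline plasma of all participants. Section 7.1 already collects 20 mL EDTA from each.
- Sequence all non-responders plus a random sample of about 100 responders, drawn without regard to later reinfection and analysed with sampling weights (225/100 = 2.25 per sampled responder on the planned numbers). This keeps about 89% of full-cohort efficiency.

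The cost is laboratory work on samples already held, with no extra visit or blood draw.

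If neither is funded, remove from Hypothesis 2.1 and the SVR model whichever of the two predictors is not measured in responders, and restrict objective 5 to participants with recurrence. That costs only wording, but gives up those questions.

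In either case, add previous treatment experience to the model's factor list.

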	drug use, daily injecting, type of drug injected, injecting equipmen
	borrowing), use of needle and syringe programs, and opioid substitution
	treatment with time-updated co-variates.
	Sample Size: Overall, based on previous reports of HCV reinfection amon
	recent PWID ³⁰ , and assuming loss to follow-up is 20% per year, it i
	estimated that the overall reinfection rate will be 8/100 p-yrs (95%CI 5.7
	10.7; 478 p-yrs of follow-up; 38 reinfections). Overall (225 with successful
	therapy, 38 reinfections), we will have 80% power to detect a hazard
	ratio (HR) of 2.47 or greater (with alpha=0.05) for a variable 509
	prevalent (e.g. ongoing injecting drug use).

Secondary Objectives:

- To evaluate the proportion of participants with undetectable HCV RNA at 12 weeks post end of treatment (SVR12) following DAA HCV therapy among PWID with chronic HCV infection and recent injecting drug use;
- 2) To evaluate the proportion of participants who complete treatment;
- 3) To evaluate the proportion of participants with undetectable HCV RNA at the end of treatment

Schedule of Assessments

Assessment / Procedure	Baseline	ETR					Follov	w-up (week	s from var	iable ETR)					
Study weeks	0	Variable	Weeks from variable ETR	12 (SVR12)	24 (SVR24)	36 (FU1)	48 (FU2)	60 (FU3)	72 (FU4)	84 (FU5)	96 (FU6)	108 (FU7)	120 (FU8)	132 (FU9)	144 (FU10)
Visit Window (Days)		+/- 14		+/- 14	+/- 14	+/- 14	+/- 14	+/- 14	+/- 14	+/- 14	+/- 14	+/- 14	+/- 14	+/- 14	+/- 14
Informed consent, medical history	х														
Behavioural survey	х														
Abbreviated behavioural survey		х		х	х	х	х	х	х	х	х	х	х	х	х
Health outcomes survey (EQ-5D-5L)	х	х		х	х	х	х	х	х	х	х	х	х	Х	х
HCV RNA testing (Local Laboratory)		χª		χª	X ^a	χ ^a	Хa	Х ^а	χª	Хa					
HCV-RNA testing (Finger-stick point of care testing)	х	х		х	х	х	х	х	х	х	х	х	х	х	х
Research Sample (10 mL EDTA plasma and Whole Blood)	x ^b	Х ^а		Xª	Х ^а	χ ^a	Xª	χ ^a	X ^a						

^a If the HCV RNA point of care test is positive or invalid or if the participant is suspected of relapse or reinfection, ^b 4ml whole Blood and 20mL EDTA at Baseline only

Schedule of Assessments - participants with post-treatment recurrence of viremia

Participants who return a positive HCV RNA finger-stick point of care test during the follow up period will be considered to have post-treatment recurrence of viremia. Participants with post-treatment recurrence of viremia following DAA treatment will also have the following tests performed at certain time points.

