The investigators have an excellent track record of conducting high quality cohort studies and clinical trials among PWID in the community¹⁹⁻²³ and prison²⁴, with high participant retention in follow-up. The investigators have developed a network of clinical sites providing HCV care in nine community-based drug treatment clinics^{20, 25}. In SHARP-C the investigators will explore the risk of HCV reinfection and treatment efficacy among recent PWID with chronic HCV and recent injecting drug use.

2. Hypotheses

Primary Hypothesis

The incidence of HCV reinfection following successful DAA therapy will be <8 per 100 person years among people with current injecting drug use.

3. Study objectives

Primary Objective

To evaluate the incidence of HCV reinfection following successful DAA therapy among people with chronic HCV infection and recent injecting drug use.

Secondary Objectives

- 1) To evaluate the proportion of participants with undetectable HCV RNA at 12 weeks post end of treatment (SVR12) following DAA HCV therapy among PWID with chronic HCV infection and recent injecting drug use;
- 2) To evaluate the proportion of participants who complete treatment;
- 3) To evaluate the proportion of participants with undetectable HCV RNA at the end of treatment.

Exploratory Objectives

- 1) To evaluate demographic, clinical and virological predictors of HCV reinfection;
- 2) To evaluate demographic, clinical and virological factors associated with SVR12;
- 3) To evaluate injecting risk behaviours during and following HCV treatment;
- 4) To evaluate HCV phylogenetic clustering and molecular epidemiology;
- 5) To evaluate the prevalence of resistance associated substitutions;
- 6) To evaluate the immunovirological changes occurring in the context of treatment, following treatment, and in the setting of post-treatment re-viremia including reinfection and relapse;
- 7) To determine the sensitivity and specificity of the Xpert® HCV Viral Load assay for HCV RNA detection in samples collected by finger-stick capillary whole-blood;

4. Participant population

Participants will be recruited from hospital-based HCV clinics and community-based drug treatment clinics in Australia, New Zealand and Canada

Inclusion criteria

- 1) Participants have voluntarily signed the informed consent form.
- 2) Be ≥18 years of age on day of signing informed consent form.
- 3) Have chronic HCV infection.
- 4) Recent injecting drug use (previous 6 months).

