7.2 Visits and procedures – Participants with post-treatment recurrence of viremia

Re-viremia baseline

 HCV RNA sequencing (Tested at the central laboratory using the research sample collected at baseline)

Re-viremia follow-up – RFU1 (2 weeks post re-viremia baseline), RFU2 (4 weeks post re-viremia baseline) and RFU3 (8 weeks post re-viremia baseline)

- HCV RNA (Finger-stick point of care testing)
- Research sample (EDTA plasma)

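### Finger-stick negatives at end of treatment and scheduled follow-up get no routine reference test, so specificity and post-treatment sensitivity cannot be validly estimated as objective 7 states

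*Protocol*

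**What the plan says.** The last exploratory objective (Protocol, Section 3, and the synopsis) reads: "To determine the sensitivity and specificity of the Xpert® HCV Viral Load assay for HCV RNA detection in samples collected by finger-stick capillary whole-blood". Section 10.1 repeats the intent: "The Xpert® HCV Viral Load assay is being evaluated as part of this study".

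The sampling rules that would have to supply the reference results are these:

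- **End of treatment, SVR12, SVR24 and FU1 to FU10 (Section 7.1).** The finger-stick test is done on everyone. The reference test is conditional, "HCV RNA testing (Local Laboratory) (Only if the HCV RNA point of care test is positive or invalid", and so is the stored specimen, "Research sample (EDTA plasma) (Only if the HCV RNA point of care test is positive or invalid".
- **Schedule of Assessments, footnote a.** This gives one further trigger that Section 7.1 leaves out: "If the HCV RNA point of care test is positive or invalid or if the participant is suspected of relapse or reinfection".
- **Baseline (Section 7.1).** The list has a finger-stick test and, with no condition on its result, "Research sample (20mL EDTA plasma & 4mL whole blood". No local-laboratory RNA test is listed at baseline. Section 10.1 assigns EDTA plasma to HCV RNA testing.
- **Re-viraemia visits RFU1 to RFU3 (Section 7.2).** The list has a finger-stick test and "Research sample (EDTA plasma", again with no condition on the result. Only participants who have already had a positive finger-stick test after treatment enter this schedule.

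Section 11 gives no outcome definition, analysis or sample size for objective 7.

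**The concern.** Sensitivity needs the reference result in people the index test calls negative, to count false negatives. Specificity needs it to count true negatives. If whether the reference is done depends on the index result, both measures are distorted by partial verification. Here the dependence is close to complete at the visits where nearly all RNA-negative observations arise. A statistical analysis plan cannot repair this, because no plasma is kept from routine negatives and there is nothing to test afterwards.

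Two things are at stake. First, an analyst who follows objective 7 literally and pools the verified pairs from scheduled visits would report figures produced by the sampling rule and not by the assay. Second, the negative finger-stick result does more than serve objective 7. It is the scheduled source of undetectable RNA at end of treatment and at SVR12, and of the last undetectable date in the midpoint rule for reinfection (Section 11). The study will have no routine check of those negatives at post-treatment viral loads.

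**Working it through.** The protocol states no figure for objective 7, so there is none to reproduce. The check asks which cells of the finger-stick by reference table can be filled at each type of visit, and then sizes the gap.

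**Step 1. Cells that can be observed**

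| Visit | Reference specimen | What can be estimated |
|---|---|---|
| Baseline | Plasma from all; all have chronic HCV | Sensitivity in untreated chronic infection, if the stored plasma is tested; essentially no RNA-negatives, so no specificity |
| End of treatment, SVR12 to FU10 | After a positive or invalid finger-stick test; also on clinical suspicion (footnote a) | Positive predictive value only |
| RFU1 to RFU3 | Plasma from all at these visits | Pairs only from people already finger-stick positive; any RNA-negatives are few and selected |

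The invalid-result trigger does not help: an invalid test is neither positive nor negative, so it adds nothing to the negative row. The suspicion trigger can verify some negatives, but those are chosen because viraemia is thought likely.

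**Step 2. Verified positives at scheduled visits**

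Sensitivity is TP/(TP+FN) and specificity is TN/(TN+FP). Among verified positives FN = 0 and TN = 0, so apparent sensitivity = TP/TP = 100% and apparent specificity = 0/FP = 0%, for any true accuracy.

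**Step 3. Size of the gap in follow-up**

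From Section 11: 478 person-years and 38 reinfections. From the Schedule of Assessments: visits every 12 weeks (84 days). Assumptions, not in the documents: full attendance, one viraemic visit per reinfection, relapse ignored, true sensitivity 90 to 100%, true specificity 98 to 99.9%.

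- Follow-up tests: 478 / (84/365.25) ≈ 2,078.
- RNA-negative tests: 2,078 − 38 = 2,040.

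| True sensitivity / specificity | TP | FN, unverified | FP | TN, unverified | Verified positives | PPV |
|---|---|---|---|---|---|---|
| 90% / 98% | 34.2 | 3.8 | 40.8 | 2,000 | 75 (3.6%) | 0.46 |
| 90% / 99.9% | 34.2 | 3.8 | 2.0 | 2,038 | 36 (1.7%) | 0.94 |
| 100% / 98% | 38.0 | 0 | 40.8 | 2,000 | 79 (3.8%) | 0.48 |
| 100% / 99.9% | 38.0 | 0 | 2.0 | 2,038 | 40 (1.9%) | 0.95 |

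So 36 to 79 tests are positive and verified, while 2,000 to about 2,040 true negatives and 0 to 4 false negatives have no routine reference. The positive predictive value runs from 0.46 to 0.95.

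**Step 4. What baseline can give**

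Section 6 plans 250 participants, so there are up to 250 pairs. With 250/250 detected, the exact two-sided 95% lower limit is 0.025^(1/250) = 98.5%. With 245/250 (98.0%), the exact interval is 95.4 to 99.3%.

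**Step 5. What the re-viraemia visits can give**

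The 38 expected reinfections give at most 38 × 3 = 114 pairs, with a few more from relapses or initial false positives.

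**The case against.** The strongest reply is that the protocol provides more reference data than the scheduled-visit rule suggests. Baseline plasma is universal, RFU1 to RFU3 plasma is unconditional, footnote a allows a reference on suspicion, and a false-positive finger-stick test does receive a local RNA test. All of this is correct, and it limits the point. A reader might infer that neither measure can be estimated anywhere, that no negative is ever checked after baseline, or that the study as a whole must yield 100% sensitivity and 0% specificity. The documents do not support any of these. Baseline sensitivity is available, some negatives can be verified, and the 100% and 0% figures describe only verified positives at scheduled visits. None of the extra sources, however, gives a representative set of RNA-negative people or of post-treatment false negatives.

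A reader might also infer that the primary endpoint rests on an unverified assay and is therefore invalid. That goes too far. Positive and invalid results are to be confirmed locally, sequencing separates relapse from reinfection (Section 10.1), and reinfection requires a distinct strain (Section 19). Testing recurs every 12 weeks, so persistent viraemia missed once can be found at the next visit. The midpoint date would then move from 6 weeks before the missed visit to 6 weeks after it, 12 weeks later. No effect on the incidence rate has been quantified here. What stands is narrower: negatives are not routinely verified at post-treatment viral loads, and baseline pairs inform sensitivity only in untreated infection.

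Finally, objective 7 is exploratory and has no planned sample size. That bears on the weight of the point, but an exploratory objective should still name quantities the sampling can deliver.

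**Conclusion.** The point holds in this form: specificity, and sensitivity for post-treatment viraemia, cannot be validly estimated under the sampling rule in Section 7.1, although objective 7 says they will be. Sensitivity in untreated chronic infection and positive predictive value in follow-up can be.

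This conclusion follows from the sampling rule alone. The counts of about 2,078 follow-up tests, 1.7 to 3.8% verified as positive and about 2,000 unverified true negatives rest on the protocol's planning figures and on assumed attendance and accuracy; they show scale only. The baseline precision (lower limit 98.5% if 250 of 250 are detected) assumes that all 250 baseline plasma samples are tested and are RNA positive. The matter should be corrected, in proportion to an exploratory objective. It does not by itself invalidate the primary analysis.

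**What to change.** - Restate objective 7, in the synopsis and Section 3, as sensitivity of the finger-stick assay at baseline plus positive predictive value in follow-up, and delete specificity.
- State that the reference assay will be run on stored baseline plasma, blind to the finger-stick result, since no local RNA test is scheduled at baseline.
- State that verified pairs from end of treatment and scheduled follow-up will not be used for sensitivity or specificity, and that RFU1 to RFU3 pairs are descriptive only.
- Reconcile Section 7.1 with footnote a of the Schedule of Assessments on whether suspected relapse or reinfection also triggers the reference test and plasma.
- Add a limitation: negative finger-stick results, which supply the undetectable results at end of treatment and SVR12 and the last undetectable date for reinfection, are not routinely verified at post-treatment viral loads.

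The cost is wording plus up to 250 reference tests on plasma already being collected. Keeping specificity would need plasma from finger-stick negatives at a scheduled visit, with the venous draw, processing and shipping that entails. As a guide to its yield, about 225 RNA-negative participants (90% of 250) with no false positive would give an exact 95% interval of 98.4 to 100%. That is an optional added procedure and is not needed to correct the protocol.
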